5.3 Data Handling

The following sections provide a general description of the derived and transformed variables used to describe and analyze the data.

5.3.1 Premature Withdrawal and Missing Data

Subjects who prematurely withdraw from the study will be included in analyses up to the time of withdrawal, regardless of the duration of treatment and survival follow-up.

Missing data occurs when any requested data is not provided, leading to blank field on the collection instrument. Answers such as "Not applicable", "Not evaluable", etc. are not considered to be missing data and should be displayed as such.

For the time to event endpoints including DOR, PFS and OS, the missing data handling method will be censoring. Censoring mechanisms for these endpoints are described in Section 7.

The length of study treatment for each subject will depend on the safety, tolerability and efficacy of the treatment, so the duration of treatment will vary across subjects. Similarly, the duration of follow up for survival will also vary. All time to event endpoints will be analyzed using suitable statistical methods.

In the event that the study is prematurely discontinued, the study team will review the data to assess which statistical analyses are still considered appropriate.

5.3.2 Baseline and Change from Baseline

Unless otherwise specified, the baseline value is defined as the last value obtained on or before the date and time of the first SL-172154 dose on Cycle 1 Day (C1D1). Post-baseline values are defined as value obtained after the first dose of SL-172154.

Change from baseline is calculated as:

• Post-baseline value - baseline value

The percent change from baseline is calculated as:

• (Post-baseline value - baseline value)*100/baseline value

If either baseline or post-baseline value is missing, the change from baseline and percent change from baseline will be missing.

5.3.3 Study Day, Duration, and Time from Event

The reference date for age calculation is the date of consent form signed as age is an eligibility requirement. The reference date for safety, efficacy and other data analyses is the date of the first dose.

• Study Day – Study Day 1 is defined as the date of the first dose; the day before the first dose is defined as Study Day -1. There is no study day 0. For a given event date, Study Day is calculated relative to the date of first dose of study drug.

```
Study Day = [Event Date – First Dose Date] (in days) + 1 day, where the event date is on or after the first dose date.

Study Day = [Event Date – First Dose Date] (in days), where the event date is before the first dose date.
```

• **Duration (Days)** – A duration is calculated as the stop date minus the start date plus one.

```
Duration (days) = [Stop Date - Start Date] (in days) + 1 day.
```

- **Time since an event** -Time since an event (e.g. time since initial diagnosis) is calculated as the reference date minus the event date. For time since initial diagnosis, the reference date is the first dose of study treatment.
- **Time to an event-** Time to an event (e.g. time to response, PFS, OS) is calculated as the event date minus the reference date+1. For time to response, PFS and OS, the first dose of study treatment is the reference date.

To convert days to months, divide the number of days by 30.4375 (365.24/12) and round to one decimal place.

5.3.4 Imputation of Partial Date

In general, imputed partial dates will not be used to derive study day or duration variables, unless otherwise specified. In addition, imputed partial dates are not used for time to event endpoint analysis. However, partial dates may be imputed for exploratory analysis. The imputed partial data will be flagged in the dataset to indicate the level of imputation. Imputed dates will not be displayed in the data listings.

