To characterize the PK of SL-172154.	 Maximum observed concentration (Cmax) and time at which the maximum concentration is observed (Tmax) and minimum observed concentration (Cmin) following single and multiple doses of SL-172154 Area under the serum concentration-time curve (AUC) Terminal elimination half-life (t¹/₂), Clearance (CL) and Volume of Distribution (Vz)
Exploratory Objectives	Outcome Measures
To assess target engagement of cluster of differentiation 40 (CD40) on peripheral blood mononuclear cells (PBMCs) prior to and following SL-172154 administration. To assess target engagement of CD47 on red blood cells (RBCs) and PBMCs prior to and following SL-172154 administration.	 Free/total receptor occupancy of CD40 Free/total receptor occupancy of CD47
To assess pharmacodynamic biomarkers in blood prior to, on-treatment and following SL-172154 administration.	 Pharmacodynamic biomarkers in blood: Changes from baseline in cytokine/chemokine levels potentially including (but not confined to) interleukin (IL)-17α, interferon alpha (IFNα), tumor necrosis factor alpha (TNFα), IL-7, IL-8, IL-15, IL-10, IL-12p70, chemokine ligand CXCL9, CXCL10 Changes from baseline in cell counts and percentages of circulating immune cells including T cell subsets, B cell subsets, and myeloid cells Circulating immunoglobulin (Ig) levels Complement activation by assessment of SC5b-9 terminal fragment

Exploratory Objectives	Outcome Measures
To assess pharmacodynamic biomarkers in tumor tissue prior to, on-treatment and following SL-172154 administration.	 Pharmacodynamic biomarkers in tumor tissue including: Changes in T cells subsets, B cell subsets and myeloid cells. CD47 and CD40 expression Programmed cell death ligand 1 (PD-L1) expression
To evaluate binding of SL-172154 to RBCs	 Presence of SL-172154 on RBCs
To estimate progression-free survival (PFS) and overall survival (OS)	 PFS based on investigator assessment: time from first dose to progression by RECIST v1.1 or death, whichever comes first OS: time from first dose to death
To evaluate efficacy using immune related response criteria.	 ORR, CBR, TTR, DOR and PFS based on investigator assessment per immune Response Evaluation Criteria (iRECIST)

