3.11 Lost to Follow-up

- A participant will be considered lost to follow-up if he or she repeatedly fails to return for scheduled visits and is unable to be contacted by the study site.
- The following actions must be taken if a participant fails to return to the clinic for a required study visit:
 - The site must attempt to contact the participant and reschedule the missed visit as soon as possible and counsel the participant on the importance of maintaining the assigned visit schedule and ascertain whether the participant wishes to and/or should continue in the study.
 - Before a participant is deemed lost to follow up, the investigator or designee must make every effort to regain contact with the participant (where possible, 3 telephone calls and, if necessary, a certified letter sent to the participant's last known mailing

address or local equivalent methods). These contact attempts should be documented in the participant's medical record.

• Should the participant continue to be unreachable, he/she will be considered as lost to follow up and withdrawn from the study.

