- Follow-Up: All subjects will be contacted after discontinuing study therapy to collect survival status. Subjects should be contacted every 3 months (+/- 14 days) until approximately 18 months of follow up, death, withdrawal of consent, lost to follow-up or end of study. Contact may include clinic visit, telephone contact, email or mail to document survival status. Ľ.

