7.6 Overall Survival

The OS is defined as time from the first day of treatment to the date of death. A subject alive at the end of study or lost to follow-up will be censored for OS at the last date when the subject was known to be alive, i.e., the last date on study.

If data warrants, the median and quartiles of OS and their 95% CIs will be assessed using the Kaplan-Meier method and Brookmeyer and Crowley method, respectively. The proportion of subjects alive at 12 weeks, 24 weeks, 48 weeks, 72 weeks, and other timepoints of interest will be estimated using the Kaplan-Meier method. OS will be summarized and listed for the All Treated population.

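### The SAP has no event rule for a known death with an incomplete date, and for OS it equates last known alive with last date on study; if such cases occur, survival would tend to be overstated

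*SAP*

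**What the plan says.** **Incomplete dates.** SAP 5.3.4: "In addition, imputed partial dates are not used for time to event endpoint analysis". The next sentence adds: "However, partial dates may be imputed for exploratory analysis". No imputation rule follows.

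**Missing data.** SAP 5.3.1: "For the time to event endpoints including DOR, PFS and OS, the missing data handling method will be censoring". It refers to SAP Section 7 for the mechanisms.

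**OS.** SAP 7.6: "The OS is defined as time from the first day of treatment to the date of death". The censoring rule, for those lost to follow-up and those still living when the study ends, is that they are "censored for OS at the last date when the subject was known to be alive, i.e., the last date on study".

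**PFS and DOR.** In SAP 7.5 and Table 4, documented progression or death is the event, and lost subjects are censored at the last evaluable post-baseline disease assessment. SAP 7.4 counts death as a DOR event and uses the same censoring guidance.

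**Follow-up.** In the Protocol Section 6 schedules, survival status is collected every 3 months, with a 14-day window, by clinic visit, telephone, email or mail. Protocol 3.14 continues this for about 18 months after treatment stops. Under Protocol 3.11, contact attempts come first; a subject who stays unreachable is then handled as follows: "he/she will be considered as lost to follow up and withdrawn from the study".

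**The concern.** Survival status obtained by telephone or mail can arrive as a month and year, or only a year. The subject is certainly dead, but the analysis has no complete date. If imputation is barred and censoring is the default, a certain event can become a censored observation. That censoring is informative, because it happens only to subjects who died.

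The OS censoring wording raises a separate issue. If a lost subject is censored at study exit instead of at the last contact confirming the subject alive, time during which nobody knew the subject's status is counted as survival.

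In expectation, both effects push survival upward. The outputs could also disagree: SAP 8.4 lists and summarises all deaths, so a death could appear there and not be an event in the OS table.

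**Working it through.** **1. Trace a known death with an incomplete date through the rules.**

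- *OS.* The event needs a date of death, and an imputed one may not be used. The SAP 7.6 censoring sentence covers subjects who are alive or lost; this subject is neither. No rule applies, so what remains is the general censoring default in SAP 5.3.1, or exclusion.
- *PFS, no earlier progression.* The first row of Table 4 makes death an event on its date, which is incomplete. The row for subjects without progression or death does not describe this subject, and the row for missing assessments applies only where there is no death. Again no rule fits.
- *PFS, earlier progression documented.* The progression date is used, so the death date does not matter.
- *DOR.* The logic is the same as for PFS, in responders only.

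**2. Trace a lost subject.** For PFS, Table 4 gives a disease-assessment date, so study exit is not used. For OS, last known alive is the last successful contact. Withdrawal under Protocol 3.11 follows failed attempts, and contacts are 3 months apart, so the last date on study can be later.

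**3. Size.** The documents state no median OS, loss rate or incomplete-date rate, so there is no plan figure to reproduce. What follows is illustration.

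Assumptions: 200,000 simulated subjects; exponential OS with median 6, 9 or 12 months; follow-up to 24 months; contact every 3 months; 5%, 10% or 20% of deaths incompletely dated and censored at the last contact. The landmark is 48 weeks = 48 × 7 / 30.4375 = 11.04 months.

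| Median OS (months) | All deaths dated | 5% | 10% | 20% |
|---|---|---|---|---|
| 6 | 0.279 | 0.295 | 0.312 | 0.348 |
| 9 | 0.429 | 0.445 | 0.463 | 0.500 |
| 12 | 0.528 | 0.544 | 0.561 | 0.595 |

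The increases run from 0.295 − 0.279 = 0.016 to 0.500 − 0.429 = 0.071. Median OS rises by about 0.3 months (5.98 to 6.24) to 2.8 months (12.03 to 14.78).

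Hand check: turning a random fraction q of deaths into censorings near the time of death multiplies the hazard by (1 − q), so S becomes S^(1 − q). With S = 0.429: 0.429^0.95 = 0.448, 0.429^0.90 = 0.467, 0.429^0.80 = 0.508. The simulated values are slightly lower because censoring at the last contact also removes time at risk.

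**4. Late censoring of lost subjects (OS).** Assume 10% or 20% of subjects are selected for loss over 12 months and censored 0, 3 or 6 months after the last contact. With no delay there is no bias. With 3 to 6 months' delay, 48-week OS rises by about 0.01 to 0.02 at 10% loss (median 9: 0.428 to 0.439 and 0.448) and about 0.02 to 0.05 at 20% (median 6: 0.279 to 0.302 and 0.325).

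**5. A small group.** Take six invented deaths at 2, 4, 6, 8, 10 and 14 months, with the 6-month death censored at 3 months.

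- 48-week OS: 1/6 = 0.167 becomes 5/6 × 3/4 × 2/3 × 1/2 = 0.208.
- Median: 6 months becomes 8 months.
- 24-week OS: 4/6 = 0.667 becomes 5/6 × 3/4 = 0.625, a fall.

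**6. Effect of the remedies.** With mid-month imputation (error up to 15 days) the simulated 48-week OS returns to 0.279, 0.429 and 0.528. Censoring lost subjects at the last contact gives 0.279-0.280, 0.428-0.429 and 0.529.

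**The case against.** **PFS and OS may be exempt.** Both documents list them as exploratory objectives, so the exploratory exception in SAP 5.3.4 could apply. That reading is available. But SAP Section 7 treats PFS and OS as efficacy endpoints and uses exploratory analysis for the iRECIST versions. If PFS and OS were exempt, the bar would reach mainly TTR and DOR, which rest largely on scan dates. The exception is also optional and gives no date rule, although SAP Section 1 says analysis decisions precede database freeze. DOR is secondary, so the exception does not reach it.

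**The OS sentence leads with the right date.** Its main clause is last known alive, and nothing defines the last date on study as the withdrawal date. This stands: study exit is one reading, not the stated rule.

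**Incomplete dates can be queried.** Protocol 14.2 provides edit checks and site clarification before database lock. That lowers the number of cases but supplies no rule for those left.

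**The consequence is limited.** OS and PFS are descriptive, summarised if the data warrant it, and do not drive escalation, the MTD or sample size. The shift at 5% is small against sampling error: with an assumed 45 subjects and survival near 45%, the half-width is 1.96 × √(0.45 × 0.55 / 45) = 0.145. This stands, and it limits how much weight the point should carry.

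**Conclusion.** The gap is real and worth closing. Followed literally, the SAP may turn a known death into a censored or missing observation for OS, and for PFS or DOR where no progression was documented earlier and no Table 4 censoring rule (new therapy, or two or more missed assessments) applies. For OS only, the censoring date for a lost subject is worded so that two different dates could be used.

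The expected direction is upward if such cases occur. The size, roughly 1.5 to 7 points on 48-week OS for 5-20% incomplete death dates, rests entirely on assumed rates, exponential survival and 3-monthly contact from first dose.

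A reader might infer three stronger things that the documents do not support:

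- That these deaths can never be events. The exploratory exception leaves this open for PFS and OS.
- That lost subjects are censored at study exit throughout. Table 4 rules this out for PFS, and for OS it is only one reading.
- That survival is overstated as a matter of fact. The documents report no such cases or rates, and in a small dose group a single landmark can move down, as the 24-week figure above shows.

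**What to change.** In SAP 5.3.4, exempt death dates, so that every known death counts as an event in OS, PFS and DOR, subject to Table 4, under a pre-specified rule:

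- Month and year known: the later of mid-month and the day after last known alive.
- Year only: a pre-specified date within the possible range and not before last known alive. Setting all such deaths to the day after last known alive would shorten survival systematically, so that choice belongs in a sensitivity analysis.
- Sensitivity analyses at the earliest and latest possible dates.

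In SAP 7.6, delete the gloss that equates last known alive with the last date on study, and censor at the last documented contact confirming the subject alive.

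The cost is a few SAP sentences and slightly more analysis work. Survival estimates may become slightly less favourable.

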6. STUDY POPULATION

Unless specified otherwise, all summary tables and data listings for this section will be based on the All Treated Population.

6.1 Subject Disposition

Summaries of study population and subject disposition will include the number of subjects in each analysis population and the primary reason for end of study participation. Study population and subject disposition information will be presented in a data listing. Both summary table and listing will be based on the Screened population.

Summaries of study treatment status will include the number of subjects by treatment status, and the primary reason for study treatment discontinuation. Subject treatment discontinuation information will be presented in a data listing.

6.2 Protocol Deviations

Number of subjects for each protocol deviation type and subtype will be summarized for key deviations, non-key deviations, and all deviations, respectively. A listing with deviation details will be provided for all protocol deviations. A separate listing will be provided for subjects with inclusion and exclusion criteria deviation. Other select categories of protocol deviations including but not limited to COVID-19 related deviations may be listed or summarized.

6.3 Demographic and Baseline Characteristics

Demographic variables include age, sex, ethnicity, race, weight and height. Descriptive statistics will be presented for age, weight, and height. Frequency counts and percentages will be presented for age groups (18-<65 years, 65-<75 years and ≥75 years), sex, ethnicity, race, and baseline Eastern Cooperative Oncology Group (ECOG) score (0 or 1). All demographic and baseline characteristics data will be presented in data listings for All Treated and Screen Failure population, respectively.

6.4 Study Cancer History

Study cancer history including the type of cancer, FIGO stage at study entry, grade, World Health Organization (WHO) histologic classification of cancer, BRCA mutation status and homologous recombination deficiency (HRD) status will be summarized in a table. Time since initial diagnosis will also be summarized. All study cancer history data will be presented in a data listing.

6.5 General Medical and Surgical History

General medical history and surgical history along with start/end date and ongoing status at study entry will be presented in a data listing.

6.6 Prior Anti-Cancer Treatment

Prior study cancer systemic treatment drugs will be coded using the WHO Drug Dictionary. Prior study cancer systemic treatment including regimen number, drug name, start/end date, intent, regimen best response, and data of progression will be presented in a data listing. Time since progression on the most recent regimen, and number of prior systemic regimens will be included in the summary table.

Prior anti-cancer surgical treatment including the date and intent of procedure will be presented in a data listing.

Prior anti-cancer radiotherapy including start/end date and intent of radiotherapy will be presented in a data listing.

6.7 Study Drug Exposure

The individual subject SL-172154 administration including total dose administered, infusion concentration, infusion volume, rate of infusion, start and end time, duration of infusion, and infusion outcome for each infusion will be presented in a data listing.

Total number of doses received, duration of treatment, average dose received, and dose compliance will be summarized.

Subject average dose is calculated as the cumulative dose (mg) that a subject received divided by the total number of doses received.

Duration of SL-172154 treatment is defined as:

- Minimum of (date of death plus 1 day, data cutoff date plus 1 day, and date of last dose + 14 days if last dose is C1D15 or beyond or + 7 days if last dose is C1D1 or C1D8) minus date of first study drug administration for subjects in Schedule 1.
- Minimum of (date of death plus 1 day, data cutoff date plus 1 day, and date of last dose + 7 days) minus date of first study drug administration for subjects in Schedule 2.

In addition to mean, median, minimum and maximum, duration on treatment will also be summarized in the following categories: \leq 4 weeks, \geq 4 - 8 weeks, \geq 8 - 12 weeks, \geq 12 - 16 weeks, \geq 16 weeks.

Dose compliance is defined as the total mg of SL-172154 infused divided by the total mg of SL-172154 assigned, expressed as a percentage.

Duration of SL-172154 treatment will be plotted by subject using a horizontal bar graph with information regarding the time of first PR/CR and the first progressive disease (PD), dose level, best response (RECIST 1.1) and treatment discontinuation information for each subject.

6.8 Prior and Concomitant Medications

Prior and concomitant medications will be coded to Anatomical Therapeutic Chemical (ATC) class and Generic Drug Names using the WHO Drug Dictionary.

Prior medications are defined as medications that end prior to the date of the first dose of study treatment. Concomitant medications are defined as medications taken at any time on or after the date of the first dose of study drug. Medications that start prior to the date of the first dose but continue beyond the date of first dose will be categorized as concomitant medications. Prior and concomitant medications along with dose, route, start/end date, and indication for each medication will be presented in a data listing. If both the start and end dates are completely missing, the medication will be considered concomitant.

6.9 Concomitant Procedure

Concomitant procedures include cancer-related or treatment-related procedure or palliative radiotherapy. Concomitant procedures along with start/end date, and indication for the procedure will be presented in a data listing.

7. EFFICACY ANALYSES

The efficacy endpoints include ORR, CBR, TTR, DOR, PFS, and OS. The efficacy endpoints ORR, CBR, TTR, DOR, and PFS will be based on the investigator disease assessment per RECIST 1.1. Exploratory analyses of these endpoints will be based on the investigator disease assessment per iRECIST (iORR, iCBR, iTTR, iDOR and iPFS).

The efficacy analyses will be based on the All Treated population and/or Response Evaluable population, as appropriate. Subjects who do not have any post-baseline disease assessment will be considered as non-responders in the calculation of response rate.

Disease response will be evaluated and documented in CRF based on RECIST 1.1 until the first PD per RECIST 1.1, and then will be evaluated and documented in CRF based on iRECIST. Disease assessment will be performed at baseline (screening visit) and at the following intervals until disease progression: every 8 weeks until week 24 and every 12 weeks thereafter until year 2 and every 6 months until study conclusion. Confirmatory scans should be performed at least 4 weeks (>28 days) after initial documentation of an objective response. If subjects discontinue study treatment prior to progressive disease, they should continue to be followed with radiologic disease assessments until disease progression, start of a new anti-cancer therapy, withdrawal of consent or death, whichever is earliest.

